### **5.3. Analysis Populations**

#### **5.3.1. Intent-to-Treat/Safety Population**

The intent-to-treat (ITT) or safety population includes all subjects enrolled in the study who received at least 1 dose of any study treatment.

Demographics, baseline characteristics, subject disposition, study drug administration, and all safety and efficacy analyses will be conducted using the ITT/safety population.

#### **5.3.2. Per-Protocol Population**

Subjects in the ITT population who are considered to be compliant with the Protocol compose the per-protocol (PP) population.

The following procedures will be performed to identify those subjects who are to be excluded from the PP population prior to the database freeze:

- Clinical review of Protocol deviations/violations.
- Clinical review of concomitant medications as defined in Sections 5.9 and 5.10 of the Protocol.
- Clinical review of the drug accountability listing.

The determination of subjects being considered for exclusion from the PP population by the clinical team will be prepared and signed prior to database freeze.

The PP population may be used for sensitivity analysis of the efficacy endpoints.

### **5.3.3. Pharmacokinetic [REDACTED] valuable Population**

The PK-evaluable population will include all subjects who received at least 1 dose of study treatment and provided at least 1 postdose sample (1 PK measurement). The study pharmacokineticist will review data listings of study drug administration and sample records to identify subjects to be excluded from analyses of PK data.

## **6. BASELINE, EXPOSURE, AND DISPOSITION VARIABLES AND ANALYSES**

See [Appendix A](#) for a list of data displays.

### **6.1. Baseline**

#### **6.1.1. Demographics and Baseline Disease Characteristics**

The following demographic characteristics will be summarized and listed: age, sex, race, ethnicity, weight, height, and BMI.

Size of spleen and liver by manual palpation, and ECOG performance status at baseline will be summarized.

### **6.1.2. Disease History**

Disease history, including disease subtype and markers, time since diagnosis, results from cytogenetic testing with identification of high-risk CLL subjects, Ann Arbor staging, International Prognostic Index, and presence of B-symptoms at baseline, will be summarized and listed. For subjects with CLL or small lymphocytic lymphoma, Rai staging and markers will be summarized and listed.

Time since diagnosis will be calculated as follows:

$$\text{Time since diagnosis (years)} = (\text{Day 1 date} - \text{date of diagnosis} + 1) / 365.25$$

### **6.1.3. Prior Therapy**

Number of prior systemic therapy regimens will be summarized. Regimen name, component drugs, start and stop date, best response, reason for discontinuation, and date of relapse/progression will be listed.

Number of subjects who received prior radiation will be summarized. Radiotherapy type, body site, start and stop date, and total dose will be listed.

Number of subjects who had stem cell transplant will be summarized. Transplant date, type, source cell, setting (primary or relapse), best response, and drugs used with the transplant will be listed.

Number of subjects who had prior surgery or surgical procedure for lymphoma will be summarized. Surgery date and description of the surgery or surgical procedure will be listed.

### **6.1.4. Medical History**

Medical history will be coded to system organ class (SOC) and preferred term (PT) using MedDRA coding dictionary. Medical history will be summarized by SOC and PT and listed.

## **6.2. Disposition of Subjects**

The number and percentage of subjects who were treated, discontinued study drug, and were withdrawn from the study (with a primary reason for withdrawal) will be summarized and listed.

## **6.3. Protocol Deviations**

Protocol deviations captured on the Protocol Deviation Log will be presented in the subject data listings.

## **6.4. Exposure**

For subjects in the safety population, duration of treatment, average daily dose (mg), and dose modifications will be summarized descriptively. The summaries will be provided separately for

INCB050465 and INCB039110 when applicable. Administrations of the study drug will be listed.

- **Duration of treatment:** The number of study days from Day 1 to the last day of INCB050465 or INCB039110 taken by the subject.
- **Average daily dose (mg/day):** Total dose taken by the subject divided by duration of treatment in days.
- **Dose modifications:** Number of subjects who had dose reduction, interruption, and escalation will be summarized.

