The sponsor may implement alternative regimens such as intermediate doses, intermittent dosing schedules, BID doses, or alternative formulations, depending on PK, PD, and safety results. Based on emerging efficacy and safety data from study INCB 50465-101 as of 02 SEP 2016, 1 recommended regimen that will be evaluated in Parts 2, 3, and 6 is 20 mg QD for 9 weeks, followed by 20 mg once weekly. The 20 mg QD dose provides exposure that is approximately 2-fold greater than the IC_{90} (based on an *in vitro* whole-blood assay) at trough. Furthermore, all 11 NHL subjects who received 20 mg QD have achieved an objective response. However, 24% of all 46 subjects in study INCB 50465-101 as of 02 SEP 2016 discontinued study treatment due to an AE. Among the subjects with an objective response ($n = 20$), 7 (35%) discontinued study treatment due to an AE. Consequently, after administration of 20 mg QD for 9 weeks, the dosing regimen will be reduced to 20 mg once weekly. This once-weekly regimen is proposed to maintain response while providing time off from pathway inhibition, which may reduce the frequency of AEs. Pharmacodynamic data from INCB 50465-101 showed that a single dose of 20 mg exhibited maximal inhibition of AKT in an *ex vivo* pharmacodynamic assay, and PK modeling suggests that 20 mg once weekly will 1) achieve maximal inhibition equivalent to approximately $10 \times IC_{90}$, 2) exceed the IC_{90} for approximately 36 hours, and 3) have minimal to no inhibition for approximately half the dosing interval. This once-weekly regimen is similar to

that of another PI3K inhibitor (copanlisib), which is administered intravenously on Days 1, 8, and 15 of a 28-day cycle, and which achieved 7 objective responses in 9 subjects with non-Hodgkin lymphoma (Patnaik et al 2016). Among the 51 subjects who received study drug, 4 discontinued treatment due to an AE. There were 2 events of Grade 3 noninfectious pneumonitis, 1 event of Grade 3 diarrhea, and no events of colitis.

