5.4. Duration of Treatment and Subject Participation

Subjects in Parts 1, 2, and 3 will be treated in continuous 21-day cycles indefinitely; this may include temporary interruptions described in Section 5.6. Subjects in Part 6 will be treated in 21-day cycles. INCB050465 may continue indefinitely, but R-ICE will only be given for 3 cycles.

Subjects who have evidence of objective clinical benefit, regardless of dose level, may continue to be treated at that dose level. Dose and schedule changes may be implemented for ongoing subjects based on emerging tolerability data. If study drug is permanently discontinued (for reasons, see Section 5.6.2.1) the subject will be withdrawn from the study. Treatment duration will vary among subjects, but is expected to average approximately 6 months.

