Subjects Who Had INCB039110 Dose Reduction	xxx (xxx.x)				
From 400 mg QD to 300 mg QD	xxx (xxx.x)				
From 300 mg QD to 200 mg QD	xxx (xxx.x)				
Etc...	xxx (xxx.x)				
Compliance with INCB039110[c] (%)					
N	xxx	xxx	xxx	xxx	xxx
Mean	xx.xx	xx.xx	xx.xx	xx.xx	xx.xx
STD	xx.xxx	xx.xxx	xx.xxx	xx.xxx	xx.xxx
Min	xx.x	xx.x	xx.x	xx.x	xx.x
Median	xx.xx	xx.xx	xx.xx	xx.xx	xx.xx
Max	xx.x	xx.x	xx.x	xx.x	xx.x

PROGRAM\OUTPUT: xxxxx.SAS\xxxxx.LST

DATE (TIME) : DDMMYY (HH:MM)

[a] Duration of treatment (days) = Date of last dose - Date of first dose + 1.

[b] Average daily dose (mg/day) = [total actual dose taken (mg)] / [duration of treatment (days)].

[c] Compliance (%) = 100 × (total dose actually taken [mg]) / (total intended dose [mg]).

Reference: Listing 16.x.x.x.x

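### The SAP's average daily dose blends the daily and once-weekly phases of the 20 mg regimen and falls with time on treatment even under full adherence

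*SAP*

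**What the plan says.** SAP 6.4 (Exposure) defines average daily dose as "Total dose taken by the subject divided by duration of treatment in days". The footnotes to the shell of Table 3.1.1 in SAP Appendix A repeat this and set the denominator: "Duration of treatment (days) = Date of last dose - Date of first dose + 1". Every calendar day between first and last dose counts, whether or not a dose was due. The same section adds: "Number of subjects who had dose reduction, interruption, and escalation will be summarized". It does not define a dose reduction.

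SAP 2.1 bases the plan on Protocol Amendment 3 and keeps it in force for later amendments unless it is superseded. SAP Table 5 lists only the original version of 26 JUN 2015, and SAP 4.1.7 describes both study drugs as taken continuously.

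The current protocol has moved on. Section 1.7.1 names as one recommended regimen for Parts 2, 3 and 6 "20 mg QD for 9 weeks, followed by 20 mg once weekly", and says of the switch that "the dosing regimen will be reduced to 20 mg once weekly". Section 5.4 also allows schedule changes for ongoing subjects. On time on study it states: "Treatment duration will vary among subjects, but is expected to average approximately 6 months".

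**The concern.** Total dose over calendar days is a sensible summary when a dose is due every day: it equals the assigned dose under full adherence and drops below it only when doses are missed, held or reduced. Once the schedule changes by design from daily to weekly, that link is lost. The value then depends chiefly on how long the subject stayed on treatment after week 9.

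Protocol 1.7.1 gives the reason for the weekly phase: 24% of the 46 subjects had stopped treatment for an adverse event by the 02 SEP 2016 cut. Protocol 1.2.4 reports that all but one of those events came after the 9-week disease assessment. How much drug was actually delivered in the weekly phase is therefore what a reader of the safety results needs to know about this regimen, and one blended figure cannot show it.

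**Working it through.** The documents give no expected average daily dose, so there is no figure to reproduce. The check applies the SAP formula to a subject who takes every dose.

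**Inputs**
- Regimen: 20 mg daily for 63 days, then 20 mg every 7 days (Protocol 1.7.1).
- Formula and denominator: SAP 6.4 and the Table 3.1.1 footnotes.
- Time points: end of the daily phase (Day 63); 104 days, the median duration at the 02 SEP 2016 cut (Protocol 1.2.4), used only as a reference point because those subjects were on daily dosing; six months, taken as 182 days (Protocol 5.4); one year.
- Assumption: the documents do not give the day of the first weekly dose, so Day 64 and Day 70 were both tried.

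**Formula.** For D days on treatment, D ≥ 63:

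average(D) = [20 × 63 + 20 × (D − 63)/7] / D = 20/7 + 1080/D

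| Day | Total dose (mg) | Average (mg/day) | Share of 20 mg/day |
|---|---|---|---|
| 63 | 1260 | 20.0 | 100% |
| 104 | 1377 | 13.2 | 66% |
| 120 | 1423 | 11.9 | 59% |
| 182 | 1600 | 8.8 | 44% |
| 365 | 2123 | 5.8 | 29% |

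The limit is 20/7 = 2.86 mg/day. Counting whole doses, with the first weekly dose on Day 64 or Day 70, changes little: 1380/104 = 13.3 or 1360/104 = 13.1; 1600/182 = 8.8 either way; 2140/365 = 5.9 or 2120/365 = 5.8.

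Solving for D, the average passes 10 mg/day at 1080/(10 − 20/7) = Day 151, 9 mg/day at Day 176 and 6 mg/day at Day 344.

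**Does the figure pick up missed weekly doses?** Take the first weekly dose on Day 70 and the last on Day 182. That is (182 − 70)/7 + 1 = 17 weekly doses, 80 doses in all, 1600 mg planned. Suppose 8 of the 17 are not taken.
- SAP average: 72 × 20 / 182 = 1440/182 = 7.9 mg/day.
- A subject who missed nothing shows the same 7.9 at D = 1080/(1440/182 − 20/7), about Day 214.

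Losing nearly half the weekly doses thus looks the same as about one more month of perfect adherence.

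**By phase, the same subject shows:**
- daily phase: 20 mg/day;
- weekly phase: 9 × 20 / 17 = 10.6 mg/week against 20 planned, a relative dose intensity of 53%;
- overall relative dose intensity: 1440/1600 = 90%.

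A fully adherent subject shows 20 mg/day, then 20 mg/week, and 100% at any duration.

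**The case against.** The strongest reply is that the average is true as far as it goes, since drug taken per calendar day does fall on weekly dosing, and that the rest of the plan guards against misreading it. Much of that stands.

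- **Adherence.** A reader might infer that a fully adherent subject will look non-adherent. The documents do not support this. Compliance (SAP 6.5) divides by the dose prescribed, stays at 100% in both phases, and sits in the same table. It does not fully replace dose intensity, because its denominator allows for dose modifications and SAP 6.4 lists interruptions among these. Doses held on the investigator's order would leave compliance at 100%.
- **Intolerance.** A reader might infer that the planned switch will be counted as a dose reduction and overstate intolerance. No SAP text says so. Protocol 1.7.1 speaks of the regimen being reduced, and the 20 mg dose itself does not change. Reductions due to a treatment-emergent adverse event are tabulated separately (SAP 8.2.3; Table 3.2.17). What remains is an undefined term in one row of Table 3.1.1.
- **Comparability.** No comparison between subjects and no hypothesis test is planned (Protocol 4.4 and 9.3), and data are summarized by the regimen initially assigned (Protocol 9.4.1). The expansion-cohort stopping rule uses Cycle 1 toxicities, before the week-9 switch. No rule uses average daily dose.
- **Transparency.** Treatment duration is in the same table and administrations are listed, so a careful reader could see why the average is low.

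None of this makes the blended figure informative about either phase.

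**Conclusion.** The point holds as a minor flaw in a descriptive summary. For subjects on 20 mg daily then weekly, the SAP formula gives a number driven by time on treatment: 20.0 mg/day at Day 63 and 8.8 at six months, 44% of the daily-phase value with no dose missed. No single range describes the effect. Values of 6 to 9 mg/day apply only between about Day 176 and Day 344; the figure is higher before and lower after.

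This rests on full adherence, a switch at exactly 63 days, and the only listed SAP version still governing. Subjects who stay on one daily schedule are unaffected. The primary safety tables, compliance and the tables of reductions due to adverse events do not depend on the formula, so a reading that the safety conclusions are compromised would go too far.

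**What to change.** In SAP 6.4 and Table 3.1.1, for subjects whose assigned schedule changes from daily to once weekly:

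1. Report duration and dose separately by phase: mg/day in the daily phase, mg/week in the weekly phase.
2. Add relative dose intensity, defined as actual cumulative dose over protocol-planned cumulative dose for the same period, by phase and overall.
3. As a clarification, state that protocol-planned schedule switches are either left out of the dose-reduction row or shown on their own line. The same sentence should say how the return to daily dosing allowed in Protocol 5.7.1 is classed, so that it is not tallied as an escalation by default.

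The existing average can stay for subjects on a single daily schedule. The cost is a short text edit and a few extra table rows. The dose records are already planned for listing (Listing 2.7.1), so no new data and no change to treatment are needed. Appendix A treats the shells as a guideline, but the definitions belong in the text of 6.4.

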## 6.5. Study Drug Compliance

For subjects in the safety population, overall compliance (%) of INCB050465 and INCB039110, when applicable, will be calculated separately as follows:

$$\text{Compliance (\%)} = 100 \times (\text{total dose actually taken [mg]}) / (\text{total intended dose [mg]})$$

Total intended dose is defined as the sum of the doses prescribed by the investigator accounting for dose modifications.

Study drug compliance will be summarized descriptively and listed.

## 6.6. Prior and Concomitant Medication

For subjects in the safety population, prior medications and concomitant medications will be coded using the WHO Drug Dictionary and summarized by WHO drug class and WHO drug term. In the data listing, each medication will be recorded as prior, concomitant, or both prior and concomitant. Results will be summarized as number and percentage of subjects with prior and concomitant medications by PT and WHO drug class.

## 7. EFFICACY

See [Appendix A](#) for a list of data displays.

### 7.1. Efficacy Hypotheses

Not applicable.

### 7.2. Analysis of the Efficacy Parameters

#### 7.2.1. Response Assessment

An objective assessment of disease status is required at baseline (screening) using a method that is appropriate for the disease subtype, per established and modified guidelines ([Hallek et al 2008](#),

Cheson et al 2014, Cheson et al 2012, Owen et al 2013). Disease status will be assessed by the site every 9 weeks following Cycle 1 Day 1. For subjects in Part 3 Expansion Cohorts, the sponsor may also have disease status assessed by a central imaging vendor.

Response status will be recorded at each postbaseline disease assessment visit as CR, VGPR (only for subjects with WM), PR, MR (only for subjects with WM), stable disease (SD), progressive disease (PD), or not evaluable (NE).

[figure not shown]
### **7.2.2. Best Overall Response and Overall Response Rate**

[figure not shown]
Best overall response is the best response recorded during the study treatment prior to and including the first PD, in the order of CR, VGPR, PR, MR, SD, PD, and NE. In the case of SD, assessment must meet the SD criteria at least once on or after Day 42. Subjects who fail to meet this criterion will have best response of PD if the next available assessment after the initial assessment indicates PD or will have best response of NE if there are no additional assessments available.

A subject is considered a responder if they have a best overall response of CR or PR (CR, VGPR, PR, or MR for subjects with WM postbaseline).

The ORR is the proportion of responders. Subjects who do not have sufficient baseline or on-study response assessment information to be adequately assessed for response status will be included in the denominators in the calculation of ORR.

Best overall response will be summarized descriptively. The ORR will be estimated with 95% CIs. Confidence intervals will be calculated based on the exact method for binomial distributions.

#### **7.2.5. Best Change in Target Lesion Size**

For subjects with measurable lesions at baseline, target lesion sizes will be measured by sum of product of diameters. The best percentage change from baseline, defined as the largest decrease in target lesion sizes during the study, will be summarized, and a waterfall plot of the best percentage change will be generated. Note that for subjects who only have increases in target lesion sizes from baseline, the smallest increase will be considered as the best change from baseline.

Target lesions considered "too small to measure" will be assigned a default value of 5 mm × 5 mm for purposes of this analysis. Likewise, target lesions identified as "not present" at postbaseline assessments will be assigned 0 mm for this analysis. In the event that a target lesion is unaccounted for in a particular postbaseline timepoint (ie, the assessment is missing or NE), then the overall sum of target lesions will not be evaluable for that postbaseline timepoint.

### **7.2.6. Change in Peripheral Blood Leukemic Cells**

For subjects with CLL, changes in peripheral blood leukemic cells, including neutrophils, platelets, hemoglobin, and lymphocytes, from baseline to each post-treatment assessment will be summarized descriptively.

## **7.3. Pharmacokinetic Analyses**

### **7.3.1. Blood Sample Collection**

Pharmacokinetic samples will be obtained at predose, 0.5, 1, 2, 4, 6, 8, and 12 (if possible) hours postdose on Cycle 1 Day 1, Cycle 1 Day 15, and Cycle 2 Day 1 (only required for subjects enrolled in the food-effect expansion cohort) and at predose on Cycle 1 Day 8. On Cycle 1 Day 1, study subjects should have fasted overnight; the clinic visit should be scheduled in the morning. A predose PK sample will be taken, followed by administration of the INCB050465 only. For subjects receiving the combination, administration of INCB039110 should be started on Day 1 after INCB050465 PK sampling is complete in Part 2 and Part 3 Cohorts C and D. On Cycle 1 Day 8 and Day 15, subjects will refrain from taking study drug in the morning before arriving at the research unit. A trough (predose) PK sample will be taken, followed by administration of the study drug. On Cycle 2 Day 1, study subjects in the expansion cohort Cohort A only will be required to undergo PK testing after fed administration on Cycle 2 Day 1 only.

### **7.3.2. Urine Sample Collection**

Urine will be collected from each subject on Cycle 1 Day 15 after morning dose and a predose void. A complete urine output collection will be collected from hour 0 (after morning dose) through 8 hours after the first dose of study drug or through 12 hours after the morning dose if a 12-hour postdose PK sample is being performed.

### **7.3.3. Bioanalytical Methodology and Analysis**

The plasma and urine samples will be analyzed for INCB050465 and INCB039110 by a validated assay and will be collected from all subjects enrolled in this study. [REDACTED]

### **7.3.4. Pharmacokinetic Analysis**

The PK calculations will be performed, if appropriate, using commercial software such as WinNonlin® (Pharsight Corporation, Mountain View, CA). Nominal times will be used in all cases, except when the difference between the actual time and nominal time is greater than 5 minutes for samples collected up to 4 hours after administration and greater than 15 minutes for samples collected more than 4 hours after administration; in these cases, actual time will be used for PK analysis. Additional details of analyses will be described in the SAP.

## **8. SAFETY AND TOLERABILITY**

See [Appendix A](#) for a list of data displays.

### **8.1. General Considerations**

Summary tables may be replaced with listings when appropriate. For instance, an AE frequency table may be replaced with a listing if it only contains a few unique PTs reported on relatively few subjects. Unless otherwise stated, table summaries will be limited to AEs occurring within 30 days of the last administration of study drug.

### **8.2. Adverse Events**

#### **8.2.1. Adverse Event Definitions**

A treatment-emergent adverse event (TEAE) is either any AE reported for the first time or the worsening of a pre-existing event after first dose of study drug. Analysis of AEs (as discussed below) will be limited to TEAEs, but data listings will include all AEs regardless of their timing to study drug administration.

Adverse events will be coded to SOC and PT using MedDRA coding dictionary. Adverse events will be tabulated by MedDRA SOC and PT. Severity of AEs will be described and graded using the National Cancer Institute CTCAE v4.03. The CTCAE reporting guidelines and grading details are available on the Cancer Therapy Evaluation Program website (<http://ctep.cancer.gov/>).

A grading (severity) scale is provided for each AE term. If the toxicity is not included in the CTCAE v4.03 criteria, it will be rated on a 1 to 4 scale as follows: (1) mild, (2) moderate, (3) severe, (4) life-threatening. All toxicities will be graded based on the worst level reached, not the level that they may have reached if they had not been treated. When the intensity of an AE changes over time for a reporting period (eg, between visits), each change in intensity will be reported as an AE until the event resolves.

The subset of AEs considered by the investigator to be related to INCB050465 or INCB039110 (when applicable) will be considered to be treatment-related AEs. If the investigator does not specify the relationship of the AE to study drug, the AE will be considered to be treatment related. The incidence of AEs and treatment-related AEs will be tabulated. In addition, serious adverse events (SAEs) will be tabulated.

Any missing onset date, causality, or severity must be queried for resolution. Unresolved missing values will be handled according to the following rules:

- An unresolved missing causality will be considered treatment related. For subjects receiving monotherapy, the event will be considered treatment related to INCB050465 only, and for subjects receiving combination therapy, the event will be considered treatment related to both investigational agents.
- An unresolved missing severity will be identified as an unknown severity.

For purposes of analysis, all AEs will be considered TEAEs unless the AE can unequivocally be defined as not treatment emergent. Therefore, a missing onset date will be considered treatment emergent, with the following examples illustrating exceptions:

- If the stop/resolution date is before the first dose date on Day 1, then the AE will not be considered treatment emergent.
- If both the month and day are missing, and the last day of the year is before the first dose date on Day 1, then the AE will not be considered treatment emergent.
- If only the day is missing, and the last day of the month is before the first dose date on Day 1, then the AE will not be considered treatment emergent.
- If only the day is missing, and the first day of the month is after the first dose date on Day 1, then the AE will be considered treatment emergent.

